**Schedule for data collection:**

In order to avoid Participant PSLC recollection-bias, Study Coordinators will use the Participant Mole Log Sheet (PMLS) and Participant taken SCI/DDI for guidance and **record** the following Datasets in REDCap Cloud:

- A) Total number of PSLCs identified by the Participant at-home
- B) Total number of PSLCs identified by the DP in-office
- C) One (1) individual SMSA output recorded in the PMLS, per target PSLC (SUSPICIOUS, UNREMARKABLE and ERROR)

Ensuring that no PHI is shared, Study Coordinators will **export** the following from the Participant smartphone/tablet gallery titled “Moles” to the Study Site smartphone/tablet gallery via Bluetooth or secure email:

- D) One (1) Participant-taken SCI, per target PSLC
- E) One (1) Participant-taken DDI, per target PSLC
- F) One (1) Participant-taken SMSA output screenshot, per target PSLC

Then, Study Coordinators will **acquire** and **export** the following from the Study Site smartphone/tablet gallery to an OHSU secure cloud storage service:

- G) One (1) Study Coordinator-taken DDI (near-perfect image technical quality) for each PSLC recorded in the PMLS and suspicious PSLCs identified by the DP in-office that were not recorded in the PMLS

Then, Study Coordinators will **upload** the DDI in Dataset (G) to the SMSA on a Study Site smartphone/tablet and **record** the following Datasets into REDCap Cloud:

- H) One (1) Study Coordinator-taken SMSA output for each PSLC, recorded in the PMLS, using Dataset (G) (SUSPICIOUS, UNREMARKABLE and ERROR), including one (1) screenshots

Then, the Study Coordinator will **record** the following Datasets into REDCap Cloud:

- I) All other SCI of suspicious PSLCs identified by the DP in-office that were not recorded in the PMLS
- J) All other DDI of suspicious PSLCs identified by the DP in-office that were not recorded in the PMLS
- K) Pathology reports for all PSLCs that were biopsied during the In-Person Phase
- L) Number of adverse events reported during the Study

-----End of In-person Phase-----

**Description of Satellite Study required activities**

Satellite Study Sites will also complete the above activities and securely **submit** their Datasets (A-L) to the Lead Study Site via OHSU secure cloud storage services. The Lead Study Site will prepare individual Qualtrics surveys using images from the Datasets above to create the following Datasets:

Dataset M) SCI triage decision (SCI-TD) based on Datasets (D) and (I), when at least two of three expert dermatologist readers have a concordant triage decision (MONITOR or BIOPSY). If there is a lack of concordance, an internationally recognized dermoscopy expert (dermatologist) will act as a fourth reader to determine the final SCI-TD

Dataset N) DDI dermoscopic diagnosis ground truth (DDI-GT) for PSLCs that were not biopsied during the In-Person Phase, using images available in Datasets (E) and (J), when at least two of three expert dermatologist readers have a concordant dermoscopic diagnosis. If there is a lack of concordance, an internationally recognized dermoscopy expert (dermatologist) will act as a fourth reader to determine the final DDI-GT

Dataset O) Histologic diagnosis ground truth (H-GT) for lesions that were biopsied during the In-Person Phase, based on evaluations using either physical or digital histologic slides (described in Sections below), when both independent expert dermatopathologists have a concordant histologic diagnosis. If there is a lack of concordance, a third internationally recognized expert dermatopathologist will determine the final H-GT.

The Study Sponsor will be responsible for Study costs (logistics, shipping, handling, research reading fees) associated with the use of either physical or digital histologic slides to create Dataset O. If digital histologic images (DHI) are chosen, the Lead Study Site will be asked to prepare DHI for their own Study Site Participants who received a biopsy during the In-person Phase. The Lead Study Site will have the option to prepare DHI for the Satellite Study Sites.

In order to eliminate biopsy specimen evaluation-bias there will not be a request to confirm or rule out any specific dermatologic neoplasm entity. All biopsy specimen slides will be de-identified and presented in blind to expert dermatopathologists at an independent Study Site for evaluation with only the following information: **Participant age, sex, skin lesion anatomic location, and a written dermatopathology request: "Please evaluate for pigmented skin lesion."**

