#### **Current standard of care for layperson at-home self-selection of PSLCs:**

In the current at-home SSE model, the layperson must first identify a specific PSL based on subjective observation. Then, the identified PSL must raise adequate concern to prompt communication with a DP through scheduling a virtual visit or requesting an in-person spot check. Currently, there is no objective prescreening method for PSLC selection or virtual visit image technical quality submission. If the layperson chooses to call and schedule an in-person visit for a new spot check appointment, the average national wait time to be seen in-person by a MD/DO dermatologist is 3 to 6 months, sometimes more. Alternatively, the layperson may choose to communicate with a DP, typically a MD/DO dermatologist, via virtual communication and send store-and-forwards SCI of their PSLC. Prior to submission, the PSLC SCI (non-medical-device assisted) image quality is not verified and often laypersons send images that are blurry, contain artifacts, or do not make it clear which PSLC is the one of concern amongst an image that contains several skin lesions (moles) in the field of view. This makes confident triage difficult for any DP in a virtual setting and often requires the DP or their team to contact the patient in order to request retaking the SCI again with better technical quality (clear image). Once an appropriate technical quality PSLC SCI is received, the DP uses non-medical-device assisted clinical judgement to make their triage decision into one of three categories:

1. **UNREMARKABLE** (no immediate concern with low clinical suspicion for malignancy, suggest the patient to self-monitor until the PSLC becomes unstable)
2. **SUSPICION** (concern with moderate to high suspicion for malignancy, recommendation to convert to an in-person visit to evaluate the PSLC with a dermatoscope, biopsy is possible)
3. **ERROR** (ask patient to retake a clear SCI image, if unsuccessful on the second attempt, convert to an in-person visit to evaluate with a dermatoscope, biopsy is possible).

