## 2.2 EXPLORATORY OBJECTIVES AND ENPOINTS

Exploratory Objectives	Endpoint	Start	End

1. To compare the accuracy of Sklip System triage when used by a layperson versus near-perfect Sklip System user
	
First, the Sensitivity of the SMSA using Study Coordinator-taken DDI (near-perfect technical quality) will be estimated to pre-specified performance goals described in sections above, using 0.05 significance level and 10% margin of error.
 
Similar to the Primary endpoint, the accuracy of SMSA output
	
First day of enrollment
	
Up to 42 days after first day of enrollment

	using Participant-taken DDI will be assessed using a 2x2 table, where the SMSA output of “SUSPICIOUS” or “UNREMARKABLE” will be compared to the SMSA output using Study Coordinator-taken DDI (near-perfect technical quality), simulating a laboratory-type environment where the SMSA is fed the best possible technical quality DDI.		
2. To assess whether Sklip System improves triage of pigmented skin lesions of concern < 6mm in diameter as suspicious as compared to the current medical provider virtual triage method that relies on store-and-forward non-medical-device assisted smartphone clinical images	Using only PSLs < 6 mm in diameter, the accuracy of the expert consensus triage decision using Participant-taken smartphone clinical images (SCI) will be assessed using a 2x2 table, where the expert consensus triage decision of “BIOPSY” or “MONITOR” will be compared to the intervention method, for both SMSA outputs recorded by Participants and SMSA outputs recorded by Study Coordinators for the same target PSLCs.	First day of enrollment	Up to 42 days after first day of enrollment
3. To assess whether Sklip System improves triage of thin melanomas with <0.8 mm Breslow depth as suspicious as compared to the current medical provider virtual triage method that relies on store-and-forward non-medical-device assisted smartphone clinical images	Using only Melanomas < 0.8 mm Breslow depth, the accuracy of the expert consensus triage decision using Participant-taken smartphone clinical images (SCI) will be assessed using a 2x2 table, where the expert consensus triage decision of “BIOPSY” or “MONITOR” will be compared to the intervention method, for both SMSA outputs recorded by Participants and SMSA outputs recorded by Study Coordinators for the same target PSLCs.	First day of enrollment	Up to 42 days after first day of enrollment

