#### *Exploratory endpoint 2*

Using only PSLs < 6 mm in diameter, the accuracy of the expert consensus triage decision using Participant-taken smartphone clinical images (SCI) will be assessed using a 2x2 table, where the expert consensus triage decision of “BIOPSY” or “MONITOR” will be compared to the intervention method, for both SMSA outputs recorded by Participants and SMSA outputs recorded by Study Coordinators for the same target PSLCs.

The Sensitivity of the SMSA output will be compared to the Sensitivity of the expert consensus triage decision of Participant-taken SCI using McNemar’s Test, given the paired nature of the data (i.e. the same PSLCs < 6mm), using 0.05 significance level.

The Specificity of the SMSA output will be compared to the Specificity of the expert consensus triage decision of Participant-taken SCI using McNemar’s Test using 0.05 significance level.

Estimates with two-sided 95% confidence intervals will be calculated using the Exact (Clopper-Pearson) method.

This will be done for each disease entity:

- Melanoma and atypical melanocytic nevi with uncertain malignant potential,
- Squamous cell carcinoma,
- Basal cell carcinoma

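### Exploratory endpoints 2 and 3 compare the device with a two-of-three expert vote, while the protocol describes current virtual triage as one provider's decision, so the result cannot be read as a comparison with current practice

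*Combined protocol and SAP*

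**What the plan says.** Section 2.2 sets the comparator for exploratory objectives 2 (lesions under 6 mm) and 3 (melanomas under 0.8 mm Breslow depth) as "the current medical provider virtual triage method that relies on store-and-forward non-medical-device assisted smartphone clinical images".

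The protocol describes that method in two places. Section 1.1 has patient-submitted images evaluated by a dermatology provider (DP). In Section 1.2, "the layperson may choose to communicate with a DP, typically a MD/DO dermatologist", and then "the DP uses non-medical-device assisted clinical judgement to make their triage decision into one of three categories". The three categories are UNREMARKABLE, SUSPICION (convert to an in-person visit, where biopsy is possible) and ERROR (retake, then an in-person visit if the retake fails).

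The analysis uses something else. For endpoint 2, Section 11.4.3 says "the accuracy of the expert consensus triage decision using Participant-taken smartphone clinical images (SCI) will be assessed", and endpoint 3 uses the same comparator. Section 3.1, Dataset M, defines the consensus as reached "when at least two of three expert dermatologist readers have a concordant triage decision (MONITOR or BIOPSY". Failing that, "an internationally recognized dermoscopy expert (dermatologist) will act as a fourth reader to determine the final SCI-TD". McNemar's test at the 0.05 level then compares SMSA with this consensus.

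**The concern.** The question concerns practice as the protocol describes it: one reader and three possible outcomes. The comparator that is analysed is an aggregate of three expert readers with two possible outcomes. Nothing in the documents justifies the panel as a stand-in for one provider, and Section 11.4.3 lists no analysis of individual readers.

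A majority vote does not have the accuracy of its average member. Its sensitivity and specificity, and so the McNemar result, depend partly on an aggregation rule that the objective does not mention. A difference from the panel, or the lack of one, would not show whether the device improves on what patients get now.

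**Working it through.** **The plan's own figures.** No sample size or power is given for endpoints 2 and 3. The overall size reproduces: 1.96² × 0.974 × 0.026 / (0.10² × 0.023) = 422.98, so 423 lesions; 423 / 1.5 × 1.10 = 310.2, so 310 participants. The present point does not depend on these figures, except for the expected case counts below.

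**Step 1: what the vote does, independent readers.** The documents give no accuracy for a single reader or a panel on smartphone images, so single-reader accuracy p is an assumption, taken over a range. The majority of three is correct with probability 3p² − 2p³:

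- p = 0.70: 3(0.49) − 2(0.343) = 0.784
- p = 0.80: 3(0.64) − 2(0.512) = 0.896
- p = 0.40: 3(0.16) − 2(0.064) = 0.352

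The vote helps above 50% and hurts below it. This applies separately to sensitivity and to specificity.

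**Step 2: correlated readers.** All three readers see the same image, so independence is the extreme case. Under a beta-binomial model with correlation ρ, set s = 1/ρ − 1, a = ps, m₂ = p(a + 1)/(s + 1) and m₃ = m₂(a + 2)/(s + 2). The majority is then correct with probability 3m₂ − 2m₃. For p = 0.70 and ρ = 0.6: m₂ = 0.616, m₃ = 0.5698, giving 0.708.

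| Single reader p | ρ = 0 | ρ = 0.3 | ρ = 0.6 |
|---|---|---|---|
| 0.30 | 0.216 | 0.268 | 0.292 |
| 0.40 | 0.352 | 0.382 | 0.395 |
| 0.60 | 0.648 | 0.618 | 0.605 |
| 0.70 | 0.784 | 0.732 | 0.708 |
| 0.792 | 0.888 | 0.828 | 0.802 |
| 0.90 | 0.972 | 0.927 | 0.907 |

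The value 0.792 is the protocol's sensitivity for primary care providers using dermoscopy. It is not a smartphone-image figure and serves only as an illustration.

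**Step 3: can it change a result?** Illustrative power of the exact two-sided McNemar test, with device sensitivity 0.974, device and reader independent given disease, and independent readers:

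- 10 melanomas (423 × 0.023 = 9.7), p = 0.60: 0.137 against one reader, 0.079 against the vote.
- 10 melanomas, p = 0.40: 0.555 against one reader, 0.668 against the vote.
- 31 melanomas and atypical nevi (10 + 21 in Table 6), p = 0.70: 0.793 against one reader, 0.473 against the vote. For endpoint 2, 31 is an upper bound, since not all will be under 6 mm.

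The choice can matter in either direction. For endpoint 3, the roughly 10 expected melanomas are of any thickness. The test needs at least 6 discordant lesions, all one way (2 × 0.5⁶ = 0.031; five give 0.0625).

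**Step 4: the outcome scale.** A positive call in Section 1.2 is conversion to an in-person visit, and an unresolved ERROR also ends in one. The panel's positive call is BIOPSY, and it has no ERROR outcome. A higher bar for a positive call would tend to lower comparator sensitivity and raise its specificity.

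**Step 5: the tie-break.** With three complete two-way reads, two must agree. The fourth reader can be reached only when a read is missing.

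**The case against.** The strongest defence is that the choice is open and pre-specified. The table in Section 2.2 places the expert consensus beside each objective, and the objective never says single; its contrast is one of method, smartphone images against the device. That is right as far as it goes: the one-reader description comes from Sections 1.1 and 1.2, not from the objective. But the objective invokes the current method, those sections are where the protocol says what that method is, and pre-specifying a different comparator does not make it represent current practice.

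A reader might infer that the panel is simply a stronger reader, so that the comparison is tilted against the device. The documents do not support this. It requires single-reader accuracy above 50%, which is unknown for small lesions and thin melanomas photographed from twelve inches. The gain nearly vanishes when readers are highly correlated, and the BIOPSY threshold can push the other way. If the panel were stronger, the comparison would be conservative for a claim of improvement.

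Two other inferences also go too far. Nothing says that individual reads are discarded; the plan only omits an analysis of them. Nor is the fourth-reader rule useless, since a missing read could leave a one-to-one split.

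It is also fair to say that per-reader results would still be experts' two-way calls. That stands, and it limits what the fix achieves.

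**Conclusion.** The mismatch holds: the comparator in endpoints 2 and 3 is not the current virtual triage that the protocol describes, so the result cannot be presented as a comparison with current practice. The size of the vote effect is unknown. Over assumed single-reader accuracy of 0.30 to 0.90 it runs from −8.4 points (0.30 to 0.216) to nearly +10 points (0.80 to 0.896) if readers are independent, and is about one point or less either way at a correlation of 0.6. The net direction, once the outcome scale is included, is undetermined. These figures rest on assumed reader accuracy, equally accurate readers and the beta-binomial form of correlation.

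The consequence is limited. Both endpoints are exploratory with no stated power, and Section 11.4.2 does not use Dataset M, so the primary endpoint is unaffected.

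**What to change.** In Section 11.4.3, endpoints 2 and 3:

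- Report each reader's sensitivity and specificity (sensitivity only for endpoint 3), and the average over the three readers of the paired SMSA-minus-reader difference. Make this the comparison that answers the objective. It removes the vote effect whichever way it runs.
- For endpoint 2, give a 95% confidence interval by bootstrap over participants, since a participant may contribute several lesions. For endpoint 3, give per-reader counts with exact intervals; with about 10 melanomas expected in total, a bootstrap would be unstable.
- Keep the consensus result as a row labelled three-expert panel.
- State as limitations that the readers are experts, and that MONITOR/BIOPSY does not match the three outcomes in Section 1.2.

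As a minor wording point, Dataset M could say that the fourth reader applies when a read is missing. Deleting the rule is not needed.

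The cost is SAP wording and a little more analysis. The two-of-three rule already requires three separate reads, and Section 3.1 plans individual surveys, so no new data are needed. The results may still not represent ordinary providers.

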#### **Current evaluation of PSLCs by the Sklip System:**

The Sklip System may safely improve triage of layperson self-selected PSLCs in an at-home environment by transitioning a regulated triage tool (FDA Class 2) into the hands of laypersons.

After a PSLC is initially identified by the layperson, the SMSA (Sklip Ai), an artificial intelligence tool, uses objective modified dermoscopy Three-Point Checklist (MD3PC): (asymmetry (including atypical network), round structures and blue-white color) to triage PSLs into one of three categories:

1. **UNREMARKABLE** (no immediate concern, limited or no positive MD3PC, with low concern for malignancy or pre-malignancy, the SMSA output provides information and suggests the layperson to self-monitor the PSLC every three months, if the user does not understand the initial SMSA output result (Sklip Mole Scan Result) or the PSLC ever becomes unstable (changes), product labelling clearly instructs the user to contact a healthcare Provider for an in-person visit, biopsy is possible)
2. **SUSPICIOUS** (positive MD3PC with moderate to high concern for malignancy, the SMSA output result provides information and strongly suggests the layperson to contact a healthcare Provider for an in-person visit, biopsy is very possible)
3. **ERROR** (uploaded image does not meet SMSA criteria and an assessment of DDI cannot be made, the SMSA output result provides information how to properly retake DDI, if the user is unsuccessful after three (3) attempts, clear product labelling instructs the layperson to contact a healthcare Provider for an in-person visit, biopsy is possible)

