### 1.3 RISK/BENEFIT ASSESSMENT

In alignment with the FDA guidance mentioned above and 21 CFR 812.3(m), Sklip Inc. has determined that a clinical Study utilizing the Sklip System constitutes a **Non-Significant Risk Device Study**. From a high level, and as described in more detail following, this is because:

1. The Sklip System is not of substantial importance in diagnosing, curing, mitigating or treating disease.
2. The Sklip System does not act in a manner that the FDA guidance flags as being considered significant risk.
3. The Sklip System is not included in the list of devices that the FDA considers to be significant risk.

Therefore, the Sklip System and the Study of it can be considered a Non-Significant Risk (NSR) Device Study. Our rationale is as follows, the Sklip System is not of substantial importance in diagnosing, curing, mitigating or treating disease. Instead, the Sklip System provides a stand-alone triage assessment according to a clinical accepted protocol, where the final decision to biopsy or not and diagnosis of a PSLC is intended for confirmation by a healthcare provider.

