#### **What should you do?**

- a) **Consult** this result in person with your established local healthcare provider, or

b) **Consult** this result in person with a dermatology provider by searching your geographic location within the Sklip network map. Click the **TAKE ACTION** button in this result to find a local dermatology office in the Sklip map.

c) **Consult** this result in person and **get a prioritized office visit within 14 days without the need for a referral**. Click the **TAKE ACTION** button in this result to find local dermatology offices in your area. Then click the **SKLIP NETWORK** filter button to identify a Sklip verified dermatology office.

*Costs associated with consulting your mole scan result with a healthcare provider are your financial responsibility and Sklip is not responsible for costs associated with medical care or verifying insurance coverage”*

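### Exploratory endpoints 2 and 3 score the phone-photo readers on biopsy, while the comparator named in the objectives, like the device, is defined by referral to an in-person visit

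*Combined protocol and SAP*

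**What the plan says.** Section 2.2 sets objectives 2 and 3 as whether the device improves triage of small lesions and thin melanomas "as compared to the current medical provider virtual triage method that relies on store-and-forward non-medical-device assisted smartphone clinical images".

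Section 1.2 describes both methods in parallel. In its account of the current standard of care, the positive call on a phone photo (SCI) is a "recommendation to convert to an in-person visit to evaluate the PSLC with a dermatoscope, biopsy is possible". In its account of the device, a SUSPICIOUS output "strongly suggests the layperson to contact a healthcare Provider for an in-person visit, biopsy is very possible". The labelling in Section 6.1.1 likewise tells the user to consult the result in person, and Section 1.3 describes a triage assessment "where the final decision to biopsy or not and diagnosis of a PSLC is intended for confirmation by a healthcare provider".

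Section 3.1 (Dataset M, repeated in the Synopsis) fixes the SCI triage decision "when at least two of three expert dermatologist readers have a concordant triage decision (MONITOR or BIOPSY"). No third answer is offered. Nothing in the documents tells readers what BIOPSY should mean or equates it with needing to be seen.

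Section 11.4.3, endpoint 2: "The Sensitivity of the SMSA output will be compared to the Sensitivity of the expert consensus triage decision of Participant-taken SCI using" McNemar's test at 0.05, with a matching test on specificity. Endpoint 3 uses the same sensitivity test in melanomas below 0.8 mm and has no specificity comparison.

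**The concern.** The reader arm is meant to represent current virtual triage. By the protocol's own description, a dermatologist using that method can say that a lesion must be seen without saying that it must be biopsied. Dataset M removes that answer. A reader in that position must choose between BIOPSY, which overstates the decision, and MONITOR, which understates it. A cancer entered as MONITOR counts as a reader miss, while the same action by the device counts as a hit.

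At stake is what a positive result would mean. A significant sensitivity difference in endpoint 2 could be reported as better triage of small lesions when both methods would have brought in the same cancers. The specificity test in endpoint 2 would move the other way and make the device look worse. Endpoint 3 has no specificity comparison in which such a shift could be seen. A referral call that was never recorded cannot be recovered in the analysis.

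**Working it through.** **The plan's own figures.** Formula (1) in Section 11.2: 1.96² × 0.974 × 0.026 / (0.10² × 0.023) = 422.98, so 423 lesions. Then 423 / 1.5 × 1.10 = 310.2, so 310 participants. Both reproduce. Neither was derived for endpoints 2 and 3, for which no sample size or power is given.

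**Cancer counts.** Table 6 expects 10 melanomas, 21 atypical nevi (10 + 21 = 31), 52 BCC and 121 SCC. These are totals for all lesion sizes, so they are upper limits for the subset under 6 mm, whose share is not stated. I use n = 15 to illustrate about half of 31 qualifying. For endpoint 3, n is at most about 10.

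**Model (assumptions).** Both methods have the same sensitivity S at the referral level. Their calls on a lesion share a latent normal correlation of 0.3. A share f of the cancers that the reader consensus would refer is entered as MONITOR. The test is the exact two-sided McNemar test at 0.05; the plan states neither the sidedness nor the version.

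For S = 0.95 the probability that both methods refer is 0.907. The discordant probabilities are then:

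- device positive, reader negative: 0.95 − 0.907 × (1 − f)
- device negative, reader positive: (0.95 − 0.907) × (1 − f)

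At f = 0.2 these are 0.224 and 0.034. Their difference is S × f = 0.95 × 0.2 = 0.19, which is the bias in the estimated sensitivity difference.

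Probability of rejection by full enumeration, S = 0.95:

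| Cancers | f = 0 | f = 0.1 | f = 0.2 | f = 0.3 |
|---|---|---|---|---|
| 10 | 0.0% | 0.1% | 1% | 5% |
| 15 | 0.0% | 0.7% | 7% | 24% |
| 31 | 0.1% | 9% | 43% | 77% |
| 52 | 0.7% | 26% | 75% | 97% |
| 121 | 2.2% | 67% | 99% | 100% |

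**Sensitivity to the assumptions.**

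- With independent errors, f = 0.2 gives 42% at n = 31 and 73% at n = 52. A correlation of 0.6 gives the same picture.
- With S = 0.80, the SCC and BCC goal in Section 2.1, n = 52 gives 12% at f = 0.1 and 39% at f = 0.2; n = 121 gives 29% at f = 0.1.
- f applies to the consensus. If three readers would all refer a lesion and each independently enters MONITOR with probability 0.1, the consensus is MONITOR with probability 3 × 0.1² × 0.9 + 0.1³ = 0.028. If the readers always agree, it is 0.1.

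**Endpoint 3.** Six discordant pairs all in one direction are needed for exact p < 0.05 (p = 0.031; five give 0.063). With about 10 melanomas this is uncommon. The bias in the estimated difference does not shrink with n: 0.95 × 0.1 = 9.5 percentage points at f = 0.1 and 19 at f = 0.2.

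**Specificity, endpoint 2.** Suppose both methods have 30% specificity at the referral level, errors are independent, and 20% of the readers' false-positive referrals are entered as MONITOR. Scored reader specificity becomes 1 − 0.70 × 0.8 = 44%. The exact test rejects in 23% of trials with 50 benign lesions, 52% with 110 and 84% with 220. The 220 is the all-size Table 6 total; 50 and 110 are illustrative.

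**The case against.** **The bias is not demonstrated.** The reader survey instructions are not in the documents, and MONITOR lines up with the self-monitoring advice attached to a negative call in Section 1.2. A reader who wants the lesion seen may decline to enter MONITOR and choose BIOPSY. Then f = 0 and nothing is lost. This stands. Section 1.1 does say that photo review gives low confidence and many conversions to in-person visits, which makes an unmet need for a referral answer plausible. It gives no figure for cancers.

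**Biopsy has a basis in the plan.** Section 2.1 names lesions that require biopsy as the detection target. That defines the condition used to count cases, not the action behind a SUSPICIOUS call or behind current virtual triage. It does not supply the missing mapping.

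**McNemar's test is not at fault.** Section 11.4.3 compares the SMSA with the consensus decision as Dataset M defines it. If those two sensitivities differ, rejection is correct. This also stands. A reader might infer that the type I error of the planned test is inflated. The documents do not support that. The issue is whether the tested comparison answers the stated objective.

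**The larger rates use generous counts.** At n = 15 and f = 0.1 rejection is 0.7%, and a sensitivity of 80% roughly halves the f = 0.1 effect at n = 52 and n = 121. Both points are correct.

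**Conclusion.** The mismatch is in the text: the comparator in objectives 2 and 3 is defined by referral, and its readers are scored on biopsy recommendation. Whether this distorts the results, and by how much, depends on f, which the documents do not give and which could be zero. Under the stated assumptions (95% referral sensitivity for both methods, latent correlation 0.3, exact two-sided test), rejection at f = 0.1 and 0.2 runs from 0.7% and 7% at n = 15 to 26% and 75% at n = 52. The n of 31 and 52 are ceilings for lesions under 6 mm.

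Three stronger readings are tempting and go too far. It is not established that the readers work at a stricter threshold than current practice. Endpoint 3 should not be expected to reject falsely: the exact test stays at about 5% or below up to f = 0.3, so the concern there is a biased sensitivity difference. And the primary performance-goal analysis is untouched, because it does not use Dataset M. Both endpoints are exploratory, so this is a worthwhile low-cost correction, not a threat to the trial's main conclusion.

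**What to change.** In the Dataset M survey (Section 3.1 and Synopsis), add an answer for in-person evaluation, for example MONITOR / IN-PERSON EVALUATION / BIOPSY. This adapts the self-monitor versus in-person split in Section 1.2. The labels are not that section's own, which are UNREMARKABLE, SUSPICION and ERROR. Define a positive SCI triage decision as IN-PERSON EVALUATION or BIOPSY, and judge two-of-three agreement on that positive/negative split. Use this definition for endpoints 2 and 3 in Sections 2.2 and 11.4.3, and report the BIOPSY-only cut descriptively.

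The cost is one survey option and a few words in the protocol and analysis plan, with no extra readers, images or participants. The downside is that the photo comparator becomes more sensitive, so any apparent device advantage in sensitivity will probably shrink. If the reads are complete, a re-read by the same readers would be needed. If that is not possible, state that the comparison is device referral against reader biopsy recommendation.
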